5.0 Study Design and Statistical Analysis Plan

- 5.1 *Describe the basic study design/approach (e.g., qualitative study using five focus groups of first year students to describe assimilation into the university community; randomized controlled trial of a behavioral change intervention to increase dietary intake of whole grains; pre- post-test evaluation of new pedagogical techniques to improve adult literacy):*

A total of 80 participants will be enrolled in study procedures. We will examine the interaction of ultrasound parameters through repeat testing of set parameters of low-intensity focused ultrasound (LIFU) while administering transcranial magnetic stimulation (TMS) to generate motor evoked potentials (MEP) which will be detected by electromyography (EMG). This study will be collected through multiple study visits. Visit 1 includes anatomical scans which will include 3T MRI and CT scans. Additional study visits will consist of LIFU/TMS parameter testing. It is anticipated participants will complete 7 study sessions, depending on participant availability.

- 5.2 *Describe corresponding data analysis plan/approach (e.g., content analysis of focus group transcripts; descriptive analysis followed by linear regression modeling; nonparametric analysis of pre- and post-test measures):*

MEP and SEP amplitude data will be analyzed separately using 4-way ANOVAs (intensity \times 3, duty cycle \times 6, duration \times 3, PRF \times 4) to determine significant main effects and interactions. Interactions will be decomposed using appropriate post-hoc examination (2/3-way ANOVA, t-tests, Tukey etc.). We will also employ stepwise regression. Iterative linear, quadratic and polynomial models will be tested for fit. Phase-plane diagrams will be produced for significant models.

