In addition to settings listed above, the following parameters are to be tested in this study. 3 Intensity (I) settings (6, 12, and 24 W/cm²), 6 duty cycle (DC) settings ranging from 1-70%, 3 duration (Dur) settings ranging from 100ms-1s, and 4 pulse repetition frequency (PRF) settings ranging from 10-1000Hz. As this is a parametric design, we are testing 216 ultrasound settings. Though each setting will take less than 1 minute to test, testing is

expected to be divided between 6 study sessions (up to 36 per session) to reduce burden to the participant.

These levels of energy are adhered to in human ultrasonic neuromodulation studies though there are no specific guidelines for energy deposition for ultrasonic neuromodulation and indeed, explicit expository and dosimetry for diagnostic and therapeutic applications, despite their prevalence and long history, has proven challenging and is still largely lacking. Ultrasound for transient neuromodulation is different from the use of ultrasound for surgery where very high intensities are used to thermally ablate tissues or for blood-brain barrier (BBB) opening where high intensities are also used in combination with contrast agents to intentionally produce cavitation as a means of opening the BBB. To date, a total of $N = 179$ in 8 published studies of healthy neurologically intact participants (plus one 1 TBI patient) have undergone a variant of LIFU for neuromodulation with no published report of severe adverse events. We have published on minor adverse events from LIFU ([name] et al. 2020).

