14.0 Number of Subjects

- 14.1 Indicate the total number of subjects to be enrolled and how this number was determined (e.g., sample size calculation [show], number of available subjects in a finite pool, number of tests funding award would allow):*

We anticipate enrolling 80 subjects in this study. This population size should allow for adequate statistical significance and analysis.

It is anticipated that 70 percent of participants will complete the study sessions. To account for this we anticipate enrolling 80 participants to yield approximately 56 participants.

Based upon preliminary data ($N = 5$) and only two variables (duty cycle and duration) we found maximal changes of motor evoked potential amplitudes of $46.35\% \pm 12.33$ and $-25.54\% \pm 15.56$ depending upon variable selection. Minimal changes with change of variables was 5.99 ± 7.87 . We propose an $N = 56$ and while N is not sufficient to detect a statistically significantly difference of $\sim 6\%$ an $N = 56$ is sufficient with a power of 0.8 and a $p = 0.05$ to detect a $\sim 15\%$ that we suggest is the minimal significant change that is required for potentially clinically significant change.

- 14.2 If this is a multi-site study, indicate the number of subjects to be enrolled at this site and the total to be enrolled from all sites:*

N/A

- 14.3 If applicable, indicate the number of potential subjects you expect to screen for enrollment, and the number of subjects you will need to complete the research procedures:*

It is anticipated that 70 percent of participants will complete the study sessions. To account for this we anticipate enrolling 80 participants to yield approximately 56 participants.

14.4 If the study has more than one procedure, indicate the total number of subjects to undergo each procedure separately:

It is anticipated that all participants will complete all study procedures, given subject interest.

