Investigation of Low-intensity Focused Ultrasound Parameters

NCT: NCT05134233

09/12/2024

Statistical Analysis Plan (SAP) for ClinicalTrials.gov Submission

Study Title: Investigating Neuromodulatory Effects of Low-Intensity Focused Ultrasound (LIFU) in Humans

1. Objective:

This study aims to assess the effects of varying parameters of low-intensity focused ultrasound (LIFU)—such as intensity, duration, duty cycle, and pulsing—on neuromodulation in the human brain. The primary focus is on evaluating changes in motor-evoked potential (MEP) amplitude when LIFU is applied concurrently with transcranial magnetic stimulation (TMS).

2. Study Design:

2.1 Interventions:

The study involves the application of LIFU using the following 20 parameter combinations:

- **Intensity levels:** 6 W/cm² and 24 W/cm²
- **Duty cycles:** 1%, 10%, 30%, 50%, and 70%
- **Durations:** 100 ms and 500 ms
- **Pulsing conditions:** Pulsed versus continuous delivery evaluated in 4 combinations

2.2 Study Type:

This is a fully parameterized, repeated measures design in which LIFU is delivered concurrently with TMS. Each subject experiences all combinations of LIFU parameters.

2.3 Data Collection:

- **MEP amplitude:** Measured as the peak-to-peak response for each LIFU parameter combination, with 20 stimulations per trial per subject.
- **Normalized MEP values:** Calculated by normalizing MEP amplitudes for each parameter combination to baseline (pre-LIFU) values.

3. Outcome Measures:

3.1 Primary Outcome Measure:

- **MEP Amplitude:** Normalized MEP amplitude, analyzed across the 20 parameter combinations of LIFU.

3.2 Secondary Outcome Measure:

- **Pulsed vs. Continuous Ultrasound:** Effects of pulsing on MEP amplitude will be evaluated.

4. Statistical Analysis Plan:

4.1 Power Analysis:

Based on preliminary data from a pilot study (N=5), we observed maximal changes in MEP amplitude of:

- **Excitatory effects:** 46.35% \pm 12.33%
- **Inhibitory effects:** -25.54% \pm 15.56%

- **Minimal effects:** $5.99\% \pm 7.87\%$ with less optimal parameter combinations.

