To detect a meaningful change in MEP amplitude, we calculated a required sample size of **N=56 participants**. This is sufficient to detect a **15% change** in MEP amplitude (minimum clinically significant change) with a power of **0.8** and a significance level of **p = 0.05**. This sample size may not detect minimal changes (~6%), but is adequate to capture meaningful excitatory and inhibitory effects across parameter combinations.

4.2 Assumptions Testing:

- **Normality of MEP Amplitudes:** Tested using **Bartlett's test for sphericity** ($p < 0.05$). If assumptions of normality or homogeneity of variances are violated, non-parametric tests will be used.

4.3 Primary Analysis:

- **Paired t-tests:** We will compare baseline normalized MEP values with post-intervention MEP values for each LIFU parameter combination. To control for multiple comparisons, a **Bonferroni correction** will be applied, adjusting the significance level to **p < 0.0025** ($0.05/20$).
- **Three-Way Repeated Measures ANOVA:** A 3-way repeated measures ANOVA will be performed to assess the main effects and interactions between the following factors:
 - **Intensity:** 6 W/cm² vs. 24 W/cm²
 - **Duty Cycle:** 1%, 10%, 30%, 50%, 70%
 - **Duration:** 100 ms vs. 500 ms
- **Post-hoc testing:** If significant main effects or interactions are observed, **Tukey's Honest Significant Difference (HSD) test** will be applied for pairwise comparisons. Tukey's HSD will control the family-wise error rate, ensuring reliable comparisons between parameter combinations.

4.4 Pulsed vs. Continuous Analysis:

A separate **three-way repeated measures ANOVA** will be conducted to evaluate differences between pulsed and continuous LIFU delivery. The main factors assessed will be:

- **Intensity:** 6 W/cm² vs. 24 W/cm²
- **Number of Cycles:** 35,000 vs. 75,000
- **Pulsing Condition:** Pulsed vs. Continuous

Post-hoc analyses using **Tukey's HSD** will follow if significant results are observed.

5. Handling Missing Data:

If missing data arises, participants with missing measurements for key outcomes will be excluded from specific analyses. However, where possible, **multiple imputation** methods will be used to handle missing data. Sensitivity analyses will be conducted to assess the robustness of the results in the presence of missing data.

6. Assumptions and Corrections:

6.1 Assumptions for Parametric Testing:

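### Protocol 5.2 selects regression terms and polynomial order from the data, then uses p-values from the same data to decide which models are plotted; the later SAP neither keeps nor withdraws this step

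*Protocol*

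**What the plan says.** Protocol 5.2 first plans "4-way ANOVAs (intensity \times 3, duty cycle \times 6, duration \times 3, PRF \times 4) to determine significant main effects and interactions", with interactions decomposed post hoc. It then adds: "We will also employ stepwise regression. Iterative linear, quadratic and polynomial models will be tested for fit". The output rule follows: "Phase-plane diagrams will be produced for significant models". The section gives no candidate terms, direction of selection, entry or removal threshold, maximum polynomial degree, fit criterion or validation. It also does not say how the regression handles repeated measurements on the same person.

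The two documents describe different grids. Protocol 7.3 states "As this is a parametric design, we are testing 216 ultrasound settings". SAP 2.1 states "The study involves the application of LIFU using the following 20 parameter combinations". For the joint effect of the parameters, SAP 4.3 says "A 3-way repeated measures ANOVA will be performed to assess the main effects and interactions between the following factors", namely intensity, duty cycle and duration. SAP 4.4 adds a second repeated-measures ANOVA for pulsed against continuous delivery. The SAP's Bonferroni correction (0.05/20 = 0.0025) applies to the paired t-tests. The SAP mentions no stepwise regression, polynomial fitting or phase-plane diagrams, and it does not say that they have been dropped.

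**The concern.** A term enters the model because it looks significant in these data, and the model is plotted because it is significant in these same data. The p-value from the final fit takes no account of the search, so it does not have its nominal error rate. The retained coefficients are also too large on average, since only estimates that happened to be large survive.

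This bears on the study's purpose. Protocol 2.1 wants to know which parameters change the effect and by how much, and how they interact. The ANOVAs test for effects and interactions, but the regression and its diagrams are the only planned output that gives a fitted response surface. A surface shown only when significant could reflect noise and could still guide later parameter choices.

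**Working it through.** The documents state no error rate for the regression, so there is no figure of the plan's own to reproduce. The check asks how often at least one term is kept when no parameter has any effect.

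**Inputs from the documents**
- Protocol grid: 3 × 6 × 3 × 4 = 216 settings (5.2, 7.3). Exact levels are taken from the pilot list in 3.2.
- SAP grid: 2 × 5 × 2 = 20 combinations (SAP 2.1, 4.3).
- Completers: 80 × 0.70 = 56 (Protocol 14.1).

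**Assumptions, not in the documents**
- Entry at p < 0.05. The 0.05 in Protocol 14.1 belongs to the sample-size statement, not to the stepwise rule.
- Candidate terms. On the Protocol grid, the smallest set is 4 linear terms and a full second-order model has 4 linear + 4 quadratic + 6 two-way = 14. On the SAP grid only duty cycle has more than two levels, so the sets are 3 linear terms and 3 + 1 + 3 = 7.

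**Step 1: approximation.** For k independent null terms tested at 0.05, P(at least one kept) = 1 − 0.95^k.

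| Grid | k | 1 − 0.95^k |
|---|---|---|
| Protocol | 4 | 18.5% |
| Protocol | 14 | 51.2% |
| SAP | 3 | 14.3% |
| SAP | 7 | 30.2% |

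**Step 2: simulation of the search with no true effect.** At 0.05 on the Protocol grid:
- 4 linear terms: 17–19%.
- 14 terms, centred predictors: 49% with forward entry, 51% with backward elimination.
- 14 terms, raw (collinear) predictors: 33% forward, 53% backward.

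On the SAP grid, 3 terms give 14–15% and 7 terms give 22–33%. Monte Carlo error is about 1–2 points. A looser entry threshold raises the rates: the 14-term model gives 53–79% at 0.10.

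**Step 3: size of retained effects.** A null coefficient kept because |z| > 1.96 has an average |z| of φ(1.96)/0.025 = 0.0584/0.025 = 2.34. With no true effect, the average retained coefficient is therefore about 2.3 standard errors from zero.

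**Step 4: if rows are pooled without a participant term.** Let r be the SD of person-specific slopes divided by the residual SD, with m settings per person and a standardised, balanced predictor. The slope variance is understated by a factor of about 1 + m·r². With r = 0.1 (assumed):
- Protocol grid: 1 + 216 × 0.01 = 3.16. A nominal 5% test rejects with probability 2Φ(−1.96/√3.16) = 27%. Four linear terms give 1 − 0.73⁴ = 72%. With ten further terms at 5%, 1 − 0.73⁴ × 0.95¹⁰ = 83%. Simulation gives 70–73% and about 80%; pooling also inflates the residual SD slightly, so the 14-term formula runs a little high.
- SAP grid: 1 + 20 × 0.01 = 1.20. The test rejects 7.4% of the time. Three terms give 1 − 0.926³ = 20%, and seven give 1 − 0.926³ × 0.95⁴ = 35%.

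**The case against.** The strongest reply has four parts.

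1. **The regression is supplementary.** Protocol 5.2 introduces it as an addition to the ANOVAs, and those, together with the SAP's repeated-measures ANOVAs, also test joint effects. This stands. A reader might infer that the regression is the only analysis of how the parameters act together, but the documents do not support that.
2. **The later SAP omits it.** The SAP is dated after the last amendment listed in the Protocol (05/16/2024), so the step may have been abandoned. That is possible, but neither document says so, and the Protocol text remains in force.
3. **Pooling of rows is not stated.** This stands. Section 5.2 is silent on within-participant handling in the regression, so the Step 4 figures are conditional. On the SAP grid they are also much smaller.
4. **The any-term rate is largely a multiplicity figure.** Testing 14 prespecified terms once each at 0.05, with no search, also gives about 51%. This stands and shapes the remedy: prespecifying the model without controlling multiplicity would leave that rate almost unchanged. It does not rescue the search, which also invalidates the p-values of the final model and inflates its coefficients.

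**Conclusion.** The concern holds for a supplementary analysis and should be fixed. Followed as written, Protocol 5.2 lets the same data choose the terms and certify them. At an assumed 0.05 entry threshold with no true effect, at least one term is kept in about 17% to about half of studies on the Protocol grid, and in about 14% to 30% on the SAP grid.

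A reader might infer that a false term appears in at least half of studies. That is not a floor. At 0.05 it needs about 14 nearly independent candidate terms, and the documents give neither the terms nor the threshold. With collinear raw predictors and forward entry, the same 14 terms give 33%. Rates of 70% or more at the 0.05 threshold arise here only by adding the assumptions that rows are pooled and that people differ in slope by 0.1 residual SD. Even so, every unpooled case above is well over the nominal 5%.

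**What to change.** In Protocol 5.2 and the SAP, replace the stepwise and iterative fitting with one prespecified mixed model that uses only the factors actually tested:

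- **Terms.** For the SAP grid: intensity, log duty cycle (linear and quadratic), duration, and the two-way interactions of the three factors, 7 terms in all. PRF is not a factor in the SAP's 20 combinations and should not appear in the model for that grid.
- **Participants.** Random intercept and slopes.
- **Error control.** A single global test, or multiplicity-adjusted term tests. As an illustration, 0.05/7 = 0.0071 per term gives 1 − (1 − 0.0071)⁷ ≈ 4.9%.
- **Model order.** If it must be chosen from the data, use leave-participants-out cross-validation.
- **Output.** Draw the fitted surface with 95% bands whether or not the model is significant.
- **Status.** Label it exploratory and supplementary to the repeated-measures ANOVA.

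If the regression has been dropped, say so in both documents; that alone would settle the point. The cost is wording, some coding, and fewer terms reported as significant. No new data are needed.

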6.0 Setting

- 6.1 *Describe the sites or locations where your research team will conduct the research. Consider each of the items listed below:*

- *Identify where your research team will identify and recruit potential subjects.*
- *Identify where the team will perform the research procedures.*
- *Describe the composition and involvement of any community advisory board(s).*
- *For research conducted in other locations, describe:*

- *Site-specific regulations or customs affecting the research at those locations.*
- *Local scientific and ethical review structure at those locations. Examples include work in other cultures or ethnic groups (within or outside of the U.S.) and work with churches. The HRPP will provide additional guidance for international research.*

Participants will be recruited from the general public in Roanoke, VA and surrounding areas. Participants will be recruited independently of other studies being conducted in the [name] lab.

All research procedures will be conducted at the Fralin Biomedical Research Institute at VTC in Roanoke, VA.

7.0 Study Intervention(s)/Investigational Agent(s)

7.1 Describe the study interventions (including behavioral interventions) and/or investigational agents (e.g., drugs or devices) to be used in this study. Consider each of the items listed below:

- *Drug/Device Handling: If the research involves drugs or devices, describe your plans to store, handle, and administer the drugs or devices so that they will be used only on subjects, and only by authorized investigators.*
- *Describe whether any of the following will be used: microwaves, X-rays, DEXA scans, general anesthesia, or sedation*
- *If control of the drugs or devices used in this protocol will be accomplished by following an established, approved organizational SOP (e.g., Research Pharmacy SOP for the Control of Investigational Drugs, etc.), please reference the SOP in this section.*

LIFU: The primary procedure involves the use of a Low-intensity focused ultrasound (LIFU) device. Ultrasound energy will be used. The device can only be activated by a computer controlled by the researchers. Study staff will be properly trained to operate this device.

TMS: The primary procedure involves the pairing of LIFU with TMS. A stimulating coil produces an electric current via electro-magnetic induction of a specific brain region to cause MEPs. Study staff will be properly trained to operate this device.

MRI: Participants will also undergo an MRI scan. Staff will review safety issues related to MRI with the subject and answer any questions. The MRI scanner used has a magnet strength of 3T, which has been approved for clinical use by the FDA. Participants will be able to communicate with study staff via an intercom. Staff operating the MRI have been trained to do so through both classroom and hands on education.

CT: Participants will undergo a head CT to obtain necessary images of their skull. CT scans will be a low-dose scan with expected radiation dose of about 2mSv. This dose gives a lifetime cancer risk of about 1 in 10,000. The lifetime natural incidence rate is about 1 in 2. Equipment will be operated by trained personnel only.

Stereotaxic Neuronavigation: Stereotaxic neuronavigation is the process of using a subject-specific anatomical MRI/CT images and co-registering them to their actual head and the LIFU transducer and TMS coil for real-time navigation of the treatment. The subject is fitted with a head-band that contains 3D infrared tracking bulbs. The LIFU transducer is also fitted with these tracking bulbs. Both the subject and treatment device are then tracked in real-time using an infrared camera. This procedure allows for precise targeting of specific brain regions using the subject-specific MRI and is wholly noninvasive. This procedure is ongoing throughout the experiment during the LIFU and TMS intervention.

- 7.2 List the name of all drugs (including any vitamins, supplements, herbs, or nicotine) to be used in the study. Indicate whether they have FDA approval, and list any limitations for their use:*

N/A

- 7.3 List all devices, how they will be used, their purpose in the study, and if they will be used in a manner consistent with their approved uses. If they will be used in ways that are not yet FDA approved, indicate whether they need an IDE or a determination that they are exempt from the IDE Determination. If a determination of significant risk or non-significant risk is needed for any of the devices, include the researcher's recommendation for each of those devices:*

LIFU: In its current state, ultrasound for neuromodulation follows the safety guidelines of the Food and Drug Administration (FDA) for obstetric diagnostic ultrasound and adult cephalic applications. The device is not FDA approved for neuromodulation. . The device has been deemed a nonsignificant risk (NSR) by the FDA. These include derated limits of spatial peak pulse average (Isppa) of 190 W/cm², a spatial peak temporal average of 720 mW/cm² (94 mW/cm² for adult cephalic) and a mechanical index (MI = peak negative pressure/ \sqrt{fc}) of 1.9. MI is an indication of the ability to produce cavitation related bio-effects and can be used as an indication for potential micromechanical damage. We will use less than 50 W/cm² (4x lower Isppa) for these studies.

In addition to settings listed above, the following parameters are to be tested in this study. 3 Intensity (I) settings (6, 12, and 24 W/cm²), 6 duty cycle (DC) settings ranging from 1-70%, 3 duration (Dur) settings ranging from 100ms-1s, and 4 pulse repetition frequency (PRF) settings ranging from 10-1000Hz. As this is a parametric design, we are testing 216 ultrasound settings. Though each setting will take less than 1 minute to test, testing is

expected to be divided between 6 study sessions (up to 36 per session) to reduce burden to the participant.

These levels of energy are adhered to in human ultrasonic neuromodulation studies though there are no specific guidelines for energy deposition for ultrasonic neuromodulation and indeed, explicit expository and dosimetry for diagnostic and therapeutic applications, despite their prevalence and long history, has proven challenging and is still largely lacking. Ultrasound for transient neuromodulation is different from the use of ultrasound for surgery where very high intensities are used to thermally ablate tissues or for blood-brain barrier (BBB) opening where high intensities are also used in combination with contrast agents to intentionally produce cavitation as a means of opening the BBB. To date, a total of $N = 179$ in 8 published studies of healthy neurologically intact participants (plus one 1 TBI patient) have undergone a variant of LIFU for neuromodulation with no published report of severe adverse events. We have published on minor adverse events from LIFU ([name] et al. 2020).

We recently compiled a qualitative report of side effects and symptoms from a subset of participants ($N = 64$) that have participated in one or more of our LIFU studies. We queried participants about their experience/tolerability with LIFU and any symptoms they experienced immediately after the intervention and also out to 22 months in a sub-cohort. There were no reports of any serious adverse events. The most common reported side effects were sleepiness, mild neck pain, headache and scalp tingling (Figure). These extinguished rapidly and no new symptoms were reported upon follow-up out to 1 month. We subsequently compared this side effect profile to other forms of non-invasive neuromodulation such as TMS, deep TMS and transcranial direct current stimulation (tDCS). We found the symptom profile to be similar to other forms of non-invasive neuromodulation. Over 300 healthy volunteers have undergone a variant of LIFU to different brain regions demonstrating that LIFU is safe and effective for transient non-invasive neuromodulation in humans.

[figure not shown]

Figure Preliminary self-report of symptoms in N = 64 healthy volunteer participants in LIFU studies in our lab ([name] et al. 2020). 'Feelings' refers to the question asking about experiencing any unusual feelings, attitudes or emotions. Please note the instance of severe 'feelings' in one individual was followed up by a neurologist and deemed unrelated to the intervention. Data excerpted from [name] et al. (2020)

As currently employed, human neuromodulation with LIFU typically involves coupling a single (or multiple) focused single-elements usually in the ~ 250 to 600 kHz range (for efficient energy transfer through skull) to the scalp to target a desired cortical brain region. Transducers for cortical targeting are generally small (~ 30 mm diameter with a ~ 30 mm focal length); produce a ~ 3-4 millimeter lateral and ~1 – 2 centimeter axial resolution, and can be placed anywhere on the head similar to other current methods of noninvasive brain stimulation.

Ultrasound is also capable of reaching brain targets deep to the cortical surface as the acoustic waves can be focused to any desired depth with certain limits. Transducers for deep brain modulation are typically larger (~ 70 mm diameter) to achieve this deeper focal length at reasonable axial resolutions. In addition to adjusting focal lengths, there are a number of parameters that can be manipulated when using ultrasound including the acoustic frequency, amplitude, duration, duty cycle, pulse repetition frequency etc. and the efficacy of some of these for successful neuromodulation has been addressed in small animal studies though the precise mechanism of acoustic energy for neuronal modulation is largely theoretical and the impact of parameter space in humans is not yet well-described. The bioeffects of ultrasound for neuromodulation in humans as described here is likely largely mechanical as opposed to thermal as the parameters used are of low intensity and duration and do not generate sufficient temperatures for thermal modulation. As described, our study does not meet any of the definitions of a significant risk device as outlined by the FDA or VT and therefore does not require an IDE.

TMS: Transcranial Magnetic Stimulation (TMS) is a neurophysiologic device that allows for non-invasive stimulation of the human brain (Rossi et al. 2009). We use the (Magstim 2002, Magstim Inc. Morrisville NC, USA). TMS is minimal risk as deemed by the FDA. Possible adverse risks are described in risk section below. During TMS, the stimulating coil is held over a subject's head and produces an electric current in the subject's brain via electro-magnetic induction. Single-pulse TMS is used to probe the state of the motor system. The TMS coil is placed over the motor cortex and a single-pulse (120% of individual maximum threshold) is conducted. This is repeated 10 – 20 times at an inter-stimulus-interval (ISI) of 5 – 10 seconds. The FDA approved TMS parameters for the treatment of major depression is 10Hz stimulation with 120% motor threshold; 4-second pulse trains; 26-second intertrain intervals, and each treatment session is last for 37.5 minutes, this is a total of 3,000 pulses. The proposed TMS parameters will stay below parameters for safety consideration.

LIFU and TMS have been paired in numerous studies in the past, resulting in no serious adverse events. Transcranial focused ultrasound neuromodulation of the human primary motor cortex (Sci Report 2018 [name] et al), Systematic examination of low-intensity ultrasound parameters on human motor cortex excitability and behavior (Elife 2020

Fomenko et al), and Time course of the effects of low-intensity transcranial ultrasound on the excitability of ipsilateral and contralateral human primary motor cortex (NeuroImage 2021 Xia et all).

MRI: Participants will receive an MRI scan. The Siemens 3T scanner has been approved by the FDA and will be used in a manner consistent with approval.

CT: Participants will receive a CT scan of their head. The Somatom Confidence RT Pro scanner has been approved by the FDA and will be used in a manner consistent with approval.

In addition to study interventional devices listed above, the following device is utilized to obtain subject data throughout the experiments.

EMG: Electromyography (EMG) involves attaching disposable surface electrodes to the skin overlying muscles of interest of the hand/ forearm in order to record muscular activity. Identification of the muscle is achieved by asking the participant to hold a light tonic contraction. The skin is prepared with a mild abrasive gel to remove surface debris and subsequently disinfected with rubbing alcohol. EMG electrodes are held in place with double-sided tape. We utilize the BrainSight device from Rogue Research.

BP: Blood pressure will be measured using the QardioArm blood pressure monitor. This is a noninvasive smart blood pressure sleeve that is placed around the arm at the bicep and is controlled through a phone app. The QardioArm is FDA approved for BP monitoring.

GSR and PPG: The galvanic skin response (GSR) sensor is used for real-time GSR biofeedback. The Shimmer GSR+ sensor monitors skin conductivity noninvasively between two reusable electrodes attached to two fingers of one hand. A stimulus causes the sweat glands to become more active, increasing moisture on the skin and allowing the current to flow more readily by changing the balance of positive and negative ions in the secreted fluid (increasing skin conductance). The Shimmer GSR+ unit also collects PPG data via an optical pulse sensor attached to a finger or earlobe.

ECG: Two ECG leads will be applied, to collect an electrocardiogram (ECG). This will noninvasively record electrical heart activity. This device will be operated by trained study staff.

Respiratory: A commercial respiration belt (SleepSense) will be wrapped around the chest to collect continuous respiration data. The belt uses Velcro closure and is noninvasive.

7.4 If the drug is investigational (has an IND) or the device has an IDE or a claim of abbreviated IDE (non-significant risk device), include the following information:

- *Identify the holder of the IND/IDE/abbreviated IDE.*

- *Explain procedures followed to comply with sponsor requirements for FDA regulated research for the following:*

FDA Regulation	Applicable to:		
	IND Studies	IDE studies	Abbreviated IDE studies
21 CFR 11	X	X	
21 CFR 54	X	X	
21 CFR 210	X		
21 CFR 211	X		
21 CFR 312	X		
21 CFR 812		X	X
21 CFR 820		X	

N/A

